#### Time to reach target Hb Range

Time to reach target Hb level of 10.0-12.0 g/dL from baseline is defined for subjects with Hb <10.0 g/dL at the baseline visit as following:

First post-treatment assessment date with value of Hb  $\geq 10.0$  and  $\leq 12.0$  g/dL – the baseline visit date +1. If target Hb level is not achieved, last Hb assessment date will be used as censored date.

A summary of time to reach target Hb level will be provided for subjects with Hb <10.0 g/dL at the baseline visit by treatment group.

A by-subject listing will be provided.

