Vadadustat treatment will stop after the dose adjustment and maintenance period has been completed (Week 16) and subjects will continue in a 2-week follow-up period (Week 17-18).

The clinical and safety assessments will be performed as described in the protocol section 9.3 and as listed in the protocol Appendix A.

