#### Hb within target Range

A summary of the number and percentage of subjects within target Hb 10-12 g/dL at the end of the dose adjustment and maintenance period (Week 16) will be provided by treatment group. In addition, the cumulative proportion of subjects within target range will be displayed graphically from baseline visit to follow up visit by treatment group.

The number and percentage of subjects above / within / below target range who are maintained within the target range at their previous visit after Week 6 will be provided by treatment group.

The effect of treatment in terms of the proportion of subjects within target Hb level at Week 6 will be analyzed using Fisher's exact test. Three post-hoc pairwise comparison, i.e., placebo vs 150 mg, placebo vs 300 mg, and placebo vs 600 mg, will be done.

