#### Rescue therapy & ESA administration

Initiation of rescue therapy will be analyzed.

The following Rescue therapy summaries will be provided:

- A summary of the number and percentage of subjects requiring rescue with RBC transfusion from baseline to the end of the primary efficacy period (Week 6) and the end of the dose adjustment and maintenance period (Week 16)
- A summary of the number and percentage of subjects requiring rescue with ESAs from baseline to the end of the primary efficacy period (Week 6) and the end of the dose adjustment and maintenance period (Week 16). An ESA rescue is defined to fulfill the following 4 criteria simultaneously:

1. ESA administration, and
2. ESA administered because the subject experienced a clinically significant worsening of their anemia or symptoms of anemia, and
3. ESA administered because the subject's Hb level is <9.0 g/dL, and
4. **Subjects' reason for early study withdrawal is because of "Worsening of anemia requiring ESA rescue or blood transfusion".**

The following ESA administration summaries will be provided:

- A summary of the number and percentage of subjects requiring administration with ESAs from baseline to the end of the primary efficacy period (Week 6) and the end of the dose adjustment and maintenance period (Week 16)

The effect of treatment in terms of the proportion of subjects requiring with RBC transfusion / ESAs administration will be analyzed using Fisher's exact test. Three post-hoc pairwise comparison, i.e., Placebo vs 150 mg, placebo vs 300 mg, and placebo vs 600 mg, will be done.

By-subject listings of rescue therapies and ESA administration will be provided by treatment group.

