#### **4.7.4 Exploratory Efficacy Variable**

##### *Time in Therapeutic Range (TTR) for Hb from week 6 to week 20*

The half-time interpolation method will be used to calculate TTR for Hb. The total time of follow-up with Hb in target range of 10.0 to 12.0 g/dL is divided by the total time. Half the time between two tests is allocated to the first Hb value, and half to the second Hb value.

A summary of TTR for Hb will be provided by treatment group.

A by-subject listing of TTR for Hb will be provided by treatment group

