#### 4.10 Determination of Sample Size

The target enrollment will be approximately 48 subjects for the study with 12 subjects enrolled in each of the 4 treatment groups.

The study is powered based on a comparison of the highest dose vadadustat group (600 mg daily) and the placebo group. Based on the results from Study AKB-6548-CI-0005 that was conducted in the United States and evaluated vadadustat in patients with anemia secondary to NDD-CKD, it is assumed that the expected mean Hb changes from

baseline to Week 6 will be approximately 0 mg/dL for the placebo group and 1.35 g/dL for the highest dose vadadustat group (600 mg daily), with a common standard deviation of 0.68 g/dL across treatment groups. With these assumptions, the study with n=12 subjects per group will have >95% power to detect the difference between treatment group and control group, at 2-sided alpha of 0.05.

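### Time to target Hb is shown by randomised group with no cut at the Week 6 placebo switch, TTR runs to a Week 20 that the study does not have, and two Fisher tests name no window.

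*SAP*

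**What the plan says.** All references are to the current SAP (Amendment 3).

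- **Design (3.1).** Treatment is fixed-dose for 6 weeks, apart from reductions for excess Hb response. Placebo subjects then switch to vadadustat, and doses are adjusted towards Hb 10.0-12.0 g/dL. Drug ends at Week 16 and follow-up covers Weeks 17 and 18.
- **Grouping (4.4.2).** Efficacy is analysed as randomised.
- **Time to target (4.7.3).** For subjects with baseline Hb below 10.0 g/dL, the event is the first post-treatment Hb within 10.0-12.0 g/dL. Otherwise: "If target Hb level is not achieved, last Hb assessment date will be used as censored date". The planned output is a summary by treatment group and a listing. No test and no estimator are named.
- **Target range (4.7.3).** The SAP adds that "the cumulative proportion of subjects within target range will be displayed graphically from baseline visit to follow up visit by treatment group". The Fisher test of target range is fixed at Week 6.
- **Rise of at least 1 g/dL (4.7.3).** Each dose is compared with placebo by Fisher's exact test. No visit or window is given.
- **RBC/ESA use (4.7.3).** Summaries are planned to Week 6 and to Week 16. The Fisher sentence then says only that the "proportion of subjects requiring with RBC transfusion / ESAs administration will be analyzed", without choosing between them.
- **Iron sufficiency (4.7.3).** The Fisher test is limited to Week 6.
- **TTR (4.7.4).** The heading reads "Time in Therapeutic Range (TTR) for Hb from week 6 to week 20". The method is half-time interpolation, and time in range is divided by total time.

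**The concern.** After Week 6 there is no placebo arm. There is a group that began on placebo and now takes vadadustat. A time-to-event rule that runs to the last Hb assessment and reports under the randomised label credits that group with responses to the drug. A reader of the placebo column would take the difference from the active columns as a dose effect, and the contamination makes that difference look smaller than it is. An off-drug value in Weeks 17-18 can also be the event, in any group.

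Time to target has its own secondary objective in section 2.2, so the display will be read.

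Two further points are simpler. TTR cannot be produced as defined, because no visit exists at its end point. The two Fisher tests could be programmed at Week 6 or over a longer period, and the choice can change the answer.

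**Working it through.** **1. The plan's own figure.** Section 4.10 assumes a mean change that "will be approximately 0 mg/dL for the placebo group and 1.35 g/dL" at 600 mg, SD 0.68, and states that "the study with n=12 subjects per group will have >95% power". The standardised difference is 1.35 / (0.68 × √(2/12)) = 4.86, so power is Φ(4.86 − 1.96) = 99.8%, or 99.6% by noncentral t with 22 df. The statement is correct. The SAP gives no figure for the secondary analyses discussed here, so what follows is illustration on stated assumptions.

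**2. Follow-up after the switch.** (18 − 6)/18 = 67% of the planned time on study.

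**3. Time to target, closed form.** Assume constant hazards, with h_p = −ln(1 − p)/6 on placebo and h_d = −ln(1 − d)/6 on drug, where p and d are the proportions at target by Week 6. At Week 16:

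- placebo never switched: 1 − exp(−16h_p)
- placebo switched at Week 6: 1 − exp(−(6h_p + 10h_d))
- active: 1 − exp(−16h_d)

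| Assumed p, d at Week 6 | Unswitched placebo | Switched placebo | Active |
|---|---|---|---|
| 15%, 60% | 35.2% | 81.5% | 91.3% |
| 29.4%, 81.1% | 60.5% | 95.6% | 98.8% |
| 41.1%, 91.2% | 75.6% | 99.0% | 99.8% |

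The Week 16 gap falls from 56 to 10 points, from 38 to 3, and from 24 to about 1. Comparing unswitched with switched separates the switch from the effect of longer follow-up. In the first row the placebo median falls from 25.6 to 9.5 weeks, against 4.5 on active.

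**4. Time to target, simulation.** The last two rows above take their Week 6 rates from this simulation. Assumptions not in the SAP: baseline Hb uniform on 8.5-9.9 or 9.0-9.9 g/dL; visits every two weeks; a linear mean rise of 1.35 g/dL by Week 6 at 600 mg, then flat; none on placebo to Week 6, then 0.5 to 1.35 g/dL over the next six weeks; total SD 0.68 split equally between subject and visit.

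| Post-switch rise, baseline range | Placebo by Wk 6 | Placebo by Wk 18 | 600 mg by Wk 6 | 600 mg by Wk 18 | Placebo events after Wk 6 |
|---|---|---|---|---|---|
| 0.5, 8.5-9.9 | 29.4% | 64.5% | 81.1% | 96.1% | 54.4% |
| 0.5, 9.0-9.9 | 41.1% | 79.5% | 91.2% | 99.1% | 48.3% |
| 1.0, 8.5-9.9 | 29.5% | 84.2% | 81.0% | 96.0% | 65.0% |
| 1.0, 9.0-9.9 | 40.9% | 93.8% | 91.2% | 99.1% | 56.4% |
| 1.35, 8.5-9.9 | 29.4% | 93.3% | 81.1% | 96.0% | 68.5% |
| 1.35, 9.0-9.9 | 41.3% | 98.2% | 91.2% | 99.1% | 58.0% |

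The gap is 50-52 points at Week 6 and 1-32 points at Week 18. Some of that narrowing would occur without a switch, as step 3 shows.

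**5. Rise of at least 1 g/dL.** On the section 4.10 inputs, the Week 6 rates are 1 − Φ(1/0.68) = 7.1% on placebo and 1 − Φ((1 − 1.35)/0.68) = 69.7% at 600 mg. Exact Fisher power with 12 per group is 87.7%. If the window ran past the switch, with the 600 mg rate held at 69.7% (later dose changes ignored), the placebo-group rate would be 1 − Φ((1 − m)/0.68) for an assumed mean rise m:

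| m (g/dL) | Placebo-group rate | Power |
|---|---|---|
| 0.5 | 23% | 53% |
| 0.75 | 36% | 28% |
| 1.0 | 50% | 9% |
| 1.35 | 70% | 2% |

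**6. TTR.** The stated window is 20 − 6 = 14 weeks: 10 on drug, 2 off drug in follow-up, and 2 after the study ends. That leaves 4/14 = 29% not on treatment.

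**The case against.** Time to target and TTR are descriptive, with no planned test against placebo. TTR is exploratory, starts at Week 6 and so lies wholly after the switch; failing to compare dose with placebo is no fault in a maintenance measure. One secondary objective concerns the dose-adjustment period, so showing data after Week 6 is legitimate. Section 4.7.1.4 calls the secondary variables supportive, with no labelling claims intended. All of this stands, and it limits the severity.

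A reader might infer that every placebo comparison runs across the switch. The SAP does not say so. The target-range and iron-sufficiency tests are fixed at Week 6, and the Week 6 rescue summary is a sound comparison. The Week 16 rescue summary spans the switch but does not pass the end of drug. For the responder and RBC/ESA tests the window is unstated, which is a gap in specification and not a stated analysis across the switch.

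A reader might also infer that a subject always in range can score at most 12/14 = 86% on TTR. That needs a fixed 14-week denominator, which section 4.7.4 does not state; half-time interpolation more naturally divides by observed time. On that reading, if the only follow-up Hb is at Week 18 (an assumption), about 1 of 12 weeks (8%) is credited to an off-drug value.

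Nor does the SAP say that censored times will be summarised as if they were observed. The summary could be a Kaplan-Meier estimate, and dropping a plot by amendment is not itself an error. A Kaplan-Meier curve would also be unaffected up to Week 6 by later events.

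What the objection does not remove is that the stated censoring rule has no cut at Week 6 or Week 16, and that the summary and the cumulative plot are presented by randomised group beyond both points.

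**Conclusion.** Wrong as written, at should-fix level. Following the time-to-target rule counts responses reached on vadadustat, and off-drug values in Weeks 17-18, as placebo-group events. The by-group summary, and the cumulative plot to the follow-up visit, then understate any dose-placebo difference after Week 6.

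That mechanism, and the 12 of 18 weeks after the switch, follow from the SAP alone. The size does not. It rests on assumed baseline Hb, visit spacing and post-switch response; within the simulated ranges, 48-69% of placebo-group events come after Week 6.

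TTR to Week 20 contradicts section 3.1. The two Fisher tests need a window, and for the responder test the choice could decide the result.

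The primary Week 6 ANCOVA, the Week 6 rescue summary and the Week 6 target-range and iron-sufficiency tests are unaffected.

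**What to change.** - **Time to target.** For the between-group display, censor at the Week 6 visit and give Kaplan-Meier estimates by group, so that the censoring date is used.
- **After Week 6.** Show time to target and the cumulative target-range plot descriptively by initial assignment, with the former placebo group labelled *placebo to vadadustat*. Mark Week 6 and Week 16 on the plot.
- **Fisher tests.** State baseline to Week 6 for the rise of at least 1 g/dL and for RBC/ESA use, matching the target-range and iron-sufficiency tests. Keep the Week 16 RBC/ESA summaries as descriptive.
- **TTR.** Define it from the Week 6 visit to the Week 16 visit, with observed time between the first and last Hb in that window as the denominator.

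The cost is SAP wording and date cut-offs in the programs. No new data are needed.

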#### Hb within target Range

A summary of the number and percentage of subjects within target Hb 10-12 g/dL at the end of the dose adjustment and maintenance period (Week 16) will be provided by treatment group. In addition, the cumulative proportion of subjects within target range will be displayed graphically from baseline visit to follow up visit by treatment group.

The number and percentage of subjects above / within / below target range who are maintained within the target range at their previous visit after Week 6 will be provided by treatment group.

The effect of treatment in terms of the proportion of subjects within target Hb level at Week 6 will be analyzed using Fisher's exact test. Three post-hoc pairwise comparison, i.e., placebo vs 150 mg, placebo vs 300 mg, and placebo vs 600 mg, will be done.

#### Increase in Hb from pre-treatment average

A summary of the number and percentage of subjects who achieved a  $\geq 1$  g/dL increase in Hb from pre-treatment average will be provided by treatment group.

The effect of treatment in terms of the proportion of subjects who achieved a  $\geq 1$  g/dL increase in Hb from pre-treatment average will be analyzed using Fisher's exact test. Three post-hoc pairwise comparison, i.e., Placebo vs 150 mg, placebo vs 300 mg, and placebo vs 600 mg, will be done.

#### Hematocrit, RBC count, and reticulocyte count

Hematocrit, RBC count, and reticulocyte count (both absolute and percent) will be analyzed as secondary efficacy variables.

The following summaries will be provided:

- A summary of hematocrit, RBC count, and reticulocyte count (both absolute and percent) by treatment group and time point. 1st and 3rd quartiles (Q1, Q3) as well as the mean, SD, median, minimum, maximum and number of observations will be presented.
- A summary of the change (absolute and percent) from baseline in hematocrit, RBC count, and reticulocyte count (both absolute and percent) by treatment group and time point
- Box plots of absolute changes from baseline in hematocrit, RBC count, and reticulocyte count (both absolute and percent) for each treatment group at each post-treatment time point

The effect of treatment in terms of the change from baseline to Week 6 in hematocrit and RBC count and reticulocyte count (both absolute and percent) will be analyzed using ANCOVA. The statistical model will assess the main effect of treatment, adjusted for baseline measurement. LS-means for each treatment and their 95% CIs will be presented. Three post-hoc pairwise comparison, i.e., Placebo vs 150 mg, placebo vs 300 mg, and placebo vs 600 mg, will be done. Unadjusted ANOVA will be performed for sensitivity.

A by-subject listing of hematocrit, RBC count, and reticulocyte count (both absolute and percent) will be provided by treatment group.

#### Iron indices and hepcidin

Iron indices (ie, iron, TIBC, TSAT, and ferritin) and hepcidin will be analyzed as secondary efficacy variables.

The following summaries will be provided:

- A summary of iron indices and hepcidin by treatment group and time point
- A summary of the change (absolute and percent) from baseline in iron indices and hepcidin by treatment group and time point
- Box plots of absolute changes from baseline in iron indices and hepcidin for each treatment group at each post-treatment time point

A by-subject listing of iron indices and hepcidin will be provided by treatment group.

#### Rescue therapy & ESA administration

Initiation of rescue therapy will be analyzed.

The following Rescue therapy summaries will be provided:

- A summary of the number and percentage of subjects requiring rescue with RBC transfusion from baseline to the end of the primary efficacy period (Week 6) and the end of the dose adjustment and maintenance period (Week 16)
- A summary of the number and percentage of subjects requiring rescue with ESAs from baseline to the end of the primary efficacy period (Week 6) and the end of the dose adjustment and maintenance period (Week 16). An ESA rescue is defined to fulfill the following 4 criteria simultaneously:

1. ESA administration, and
2. ESA administered because the subject experienced a clinically significant worsening of their anemia or symptoms of anemia, and
3. ESA administered because the subject's Hb level is <9.0 g/dL, and
4. **Subjects' reason for early study withdrawal is because of "Worsening of anemia requiring ESA rescue or blood transfusion".**

The following ESA administration summaries will be provided:

- A summary of the number and percentage of subjects requiring administration with ESAs from baseline to the end of the primary efficacy period (Week 6) and the end of the dose adjustment and maintenance period (Week 16)

The effect of treatment in terms of the proportion of subjects requiring with RBC transfusion / ESAs administration will be analyzed using Fisher's exact test. Three post-hoc pairwise comparison, i.e., Placebo vs 150 mg, placebo vs 300 mg, and placebo vs 600 mg, will be done.

By-subject listings of rescue therapies and ESA administration will be provided by treatment group.

#### Average Daily Dose

A summary of Average Daily Dose by treatment group and visit will be presented with 1st and 3rd quartiles (Q1, Q3) as well as the mean, SD, median, minimum, maximum and number of observations.

#### Dose adjustment

A overview summary of the number of dose adjustments from baseline to the end of the dose adjustment and maintenance period (Week 16) will be provided.

A summary of the number of dose adjustments by visit from baseline to the end of the dose adjustment and maintenance period (Week 16) will be provided.

A by-subject listing of dose adjustment with HB change will be provided by treatment group. The three flags of HB change will be presented as follows:

- HB > 13 g/dL at any time of study
- HB > 12 g/dL to 13 g/dL at dose adjustment and maintenance period only
- HB increase > 1 g/dL over 2 weeks at any time of study.

#### Maintenance of iron sufficiency

A summary of maintenance of iron sufficiency (defined as ferritin  $\geq 50$  ng/mL and TSAT  $\geq 20\%$ ) from baseline to the end of the primary efficacy period (Week 6) and the end of the dose adjustment and maintenance period (Week 16) will be provided.

The effect of treatment in terms of the proportion of subjects who maintain iron sufficiency will be analyzed using Fisher's exact test for week 6 only. Three post-hoc

pairwise comparison, i.e., Placebo vs 150 mg, placebo vs 300 mg, and placebo vs 600 mg, will be done.

A by-subject listing of iron sufficiency will be provided by treatment group.

#### **4.7.4 Exploratory Efficacy Variable**

##### *Time in Therapeutic Range (TTR) for Hb from week 6 to week 20*

The half-time interpolation method will be used to calculate TTR for Hb. The total time of follow-up with Hb in target range of 10.0 to 12.0 g/dL is divided by the total time. Half the time between two tests is allocated to the first Hb value, and half to the second Hb value.

A summary of TTR for Hb will be provided by treatment group.

A by-subject listing of TTR for Hb will be provided by treatment group

#### **4.8 Safety Evaluation**

All safety summaries and analyses will be based upon the safety population as defined in Section 4.4.

##### **4.8.1 Extent of Exposure**

The extent of exposure will be summarized for the safety population. The following summary will be provided.

- A summary of the treatment duration (e.g. End Date of Administration - Start date of Administration +1) by treatment group and study visits.

A by-subject listing of start, end and duration of treatment will be provided.

##### **4.8.2 Adverse Events**

AEs will be coded using the Medical Dictionary for Regulatory Activities (MedDRA) Version 19.0.

Treatment-emergent adverse events (TEAEs) will be tabulated and are defined as those AEs that either start or worsen in severity on or after the date/time of first dose of study treatment and on or before the final protocol required visit. In general, it is Week 18 Visit and 14 days after the date of last dose of study treatment. The TEAEs are defined as those adverse events that started after first injection up to 14 days post-last dose.

Where dates are missing or partially missing, AEs will be assumed to be treatment-emergent, unless there is clear evidence (through comparison of partial dates) to suggest

that the AE started prior to the first dose of study treatment or more than 14 days after the last dose of study treatment.

Partial AE and concomitant medication start dates will be imputed as follows:

1. If the year (and month and day) is unknown, the date will be imputed as the date of first intake of study treatment if this is possible (i.e., the event end date is not prior to treatment start date).
2. If the month and day is unknown then:
  - a. If the year matches the first dose date, then impute the month and day of the first dose date.
  - b. If the year is earlier than the first dose date or the first dose date is not available (subject is not dosed) and matches the year of informed consent date, then impute the month and day of the informed consent date;
  - c. Otherwise, assign January 1.
3. If the day is unknown then:
  - a. If the month and year match the first dose date, then impute the day of the first dose date.
  - b. If the month and year are earlier than the first dose date or the first dose date is not available (subject is not dosed) and matches the month and year of the informed consent date, then impute the day of the informed consent date;
  - c. Otherwise, assign '1'.

Partial AE stop dates will be imputed as follows:

1. If the year is unknown, the date will not be imputed and will be assigned a missing value.
2. If the month is unknown, then assign December.
3. If the day is unknown, then assign the last day of the month.

For all other settings (eg. year missing, but day and month available etc.), imputation strategies will be reviewed and decided in the ongoing data cleaning and sponsor meetings.

If the start and/or stop dates of medications other than study treatments are missing or partially missing, the dates will be compared as far as possible with the date of first study treatment administration.

If not specified, observed data approach will be performed.

The AE will be summarized using MedDRA system organ class (SOC) and preferred term (PT). All AE summaries will provide the number of subjects reporting at least one AE and the total number of events reported. The following summaries will be provided:

- A summary of the number and percentage of subjects reporting at least one TEAE, drug-related TEAE, TEAE leading to withdrawal, serious adverse event (SAE), drug-related SAE, SAE leading to withdrawal and death by treatment group.
- A summary of the number and percentage of subjects reporting a TEAE by treatment group, SOC, and PT
- A summary of the number and percentage of subjects reporting a drug-related TEAE by treatment group, SOC, and PT
- A summary of the number and percentage of subjects reporting a treatment-emergent SAE by treatment group, SOC and PT
- A summary of the number and percentage of subjects reporting a drug-related treatment-emergent SAE by treatment group, SOC, and PT
- A summary of the number and percentage of subjects reporting a drug-related TEAE leading to withdrawal by treatment group, SOC, and PT
- A summary of the number and percentage of subjects reporting a TEAE leading to withdrawal by treatment group, SOC, and PT
- A summary of the most common TEAEs by treatment group and PT (reported by >10% of subjects in any treatment group).
- A summary of the number and percentage of subjects reporting a TEAE by treatment group, severity, SOC and PT
- A summary of the number and percentage of subjects reporting a TEAE by treatment group, relationship, SOC and PT

AE summaries will be ordered alphabetically for SOC, and PT within SOC.

For each subject and each AE, the worst severity recorded will be attributed and used in the by-severity summaries. Similarly, the worst causality (most related to treatment) will be attributed and used in the by-causality summaries. If severity or causality is missing, data will be treated as observed

A by-subject listing of all AEs (including non-treatment-emergent events) will be provided. This listing will be presented by treatment group and will include: center, subject identifier, age, sex, race, AE (SOC, PT, and verbatim term), date of onset, date of resolution, duration, severity, seriousness, action taken, outcome and causality.

The following AEs are defined as AEs of special interest. Summaries of the number and percentage of subjects reporting the following AEs will be provided.

- PT: “hyperkalemia” (MedDRA 10020646) or “blood potassium increased” (MedDRA 10005725)
- PT: “hyperuricaemia” (MedDRA 10020903) or “blood uric acid level increased” (MedDRA 10022891)
- PT: “Hypertension” (MedDRA 10020772) or “Blood pressure increased” (MedDRA 10005750) or “Blood pressure systolic increased” (MedDRA 10005760) or “Blood pressure diastolic increased” (MedDRA 10005739) or “Blood pressure ambulatory increased” (MedDRA 10005732) or “Blood pressure inadequately controlled” (MedDRA 10051128) or “Accelerated hypertension” (MedDRA 10000358) or “Essential hypertension” (MedDRA 10015488) or “Diastolic hypertension”

- (MedDRA 10012758) or “Systolic hypertension” (MedDRA 10042957) or “Malignant hypertension” (MedDRA 10025600)
- Standardised MedDRA Query (SMQ): “Cholestasis and jaundice of hepatic origin” (SMQ 20000009) or “Drug related hepatic disorders – severe events only” (SMQ 20000007) or “Liver related investigations, signs and symptoms” (SMQ 20000008)
  - Standardised MedDRA Query (SMQ): “Ischaemic heart disease” (SMQ 20000043)
  - Standardised MedDRA Query (SMQ): “Central nervous system haemorrhages and cerebrovascular conditions” (SMQ 20000061)
  - Standardised MedDRA Query (SMQ): “Embolic and thrombotic events” (SMQ 20000081)
  - Standardised MedDRA Query (SMQ): “Cardiac failure” (SMQ 20000004)
  - Standardised MedDRA Query (SMQ): “Retinal disorders” (SMQ 20000158, narrow)

Serious adverse events that occur during the screening period and are assessed by the investigator as related to study procedures will be tabulated.

